#### **10.4. Laboratory Evaluations**

Laboratory data will be presented in separate tables for each laboratory test type (hematology, blood chemistry, coagulation, antibodies, lipids). Each laboratory parameter will be summarized by scheduled visit and by treatment group, overall SEL-212 and total, presenting actual values and change from baseline. The values from unscheduled visits will be included in analyses according to the rules set out in Section 7.4. Shift tables of the number and percentage of patients below normal range (low), within normal range (normal) and above normal range (high) at each scheduled post-baseline visit compared to the low/normal/high categorization at baseline will be provided by treatment group. A listing of clinically significant abnormal values will be provided in the tables section. Biomarkers and genetic markers will also be summarized by treatment group. Pregnancy test results and drug screen results will be listed only.

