7.1.3 Follow-Up Phase

Patients will be followed for safety monitoring (30 + 4 days) after their final study drug infusion and will have an End of Study visit by telephone at the following times: either (1) at the completion of the 6 month Treatment Phase or (2) at early termination if the patient voluntarily withdraws consent. Patients who terminate the study prematurely will continue to be followed by having all Early Termination assessments performed. Patients who terminate the study prematurely who are unable to be on-site for the Early Termination visit will be contacted by telephone for safety follow-up.

If withdrawn from study drug, regardless of reason, the patient will continue study visits to the end of Treatment Period 6.

Figure 1: Study Schematic

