13.1 Sample Size Determination

The primary efficacy criterion in this study is defined as the percentage of the patients who achieve and maintain reduction of sUA < 6 mg/dL for at least 80% of the time during Treatment Period 6 by Day 28.

The sample size estimation is based on the main estimand for the primary efficacy criterion from version 5.0 of the protocol. This estimand considered all patients who discontinue study treatment due to lack of efficacy (e.g., meeting stopping rule), due to treatment-related or non-treatment related AE as treatment failures, as well as initiating prohibited medication that lowers sUA, withdrawal of consent or lost to follow up for reasons other than COVID-19.

Based on the results in the Phase 2 study (SEL-212/201) with SEL-212, the responder rate in all randomized and dosed patients is assumed to be 45% in SEL-212. For placebo, a responder rate of 5% is assumed. Considering a randomization ratio of 1:1:1 for SEL 212A and SEL-212B against placebo, a statistical power of 90%, a two-sided alpha-level of 2.5% and using the Chi-square test with continuity correction for the 2 pairwise comparisons of each SEL-212 dose group against placebo, 32:32:32 randomized and dosed patients will be required for each treatment group. Considering the potential that some randomized patients will terminate early (approx. 8%), the number of the patients required to be randomized and dosed in total is 105 (i.e., 35:35:35) to demonstrate efficacy. For the sample size estimation, the Chi-square test is used instead of the Mantel-Haenszel test, although the randomization will be stratified for tophus presence (yes/no), as there is no valid assumption of the distribution of this stratification variable within the eligible patient population.

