13.5.3 Laboratory Assessments

Laboratory data will be summarized by the type of laboratory test and will be presented for each scheduled visit stratified by treatment group and overall. Shift tables of the number of patients with

low/normal/high (or normal/abnormal, as appropriate) values at each scheduled post-baseline visit compared to the low/normal/high (or normal/abnormal, as appropriate) categorization at baseline will be provided by treatment group and overall. Summary tables of actual values and changes from baseline will be provided for each continuous laboratory parameter at each scheduled visit by treatment group and overall.

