## 10. Safety

The population used for safety analyses will be the Safety Set (SS). All safety assessments will be listed by treatment group and patient ID. Visit-wise assessed safety parameters will be listed by treatment group, patient ID and visit/ timepoint. Unscheduled assessments will be flagged and presented in listings. Adverse events will be listed by treatment group, patient ID, start date/time and stop date/time.

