### 10.3. Adverse Events / Adverse Drug Reactions

All adverse events (AEs) will be coded using the most recent MedDRA Version. All AEs will be summarized by system organ class (SOC) and preferred term (PT) for each treatment group, for overall SEL-212 and in total. A treatment-emergent AE (TEAE) is an AE that starts or worsens at any time after initiation of study drug on Day 0 of Treatment Period 1 until the End of Study Visit (30 days after completion of the last dose of study drug).

Following AEs are considered as AESI: gout flares, infections, malignancies, viral infections, interstitial lung disease, stomatitis, infusion-related reactions including anaphylaxis, thrombosis (e.g., deep venous thrombosis, pulmonary embolism), and the following laboratory tests, if deemed clinically significant by the PI: hyperlipidemia, worsening of renal function tests, proteinuria, and leukopenia.

This document is confidential.

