**Statistical Analysis Plan**  
Sponsor: Selecta Biosciences  
Protocol No.: SEL-212/302

be repeated after at least 30 seconds and the average of the 2 readings calculated. Summary tables of the actual values and changes from baseline will be provided for each vital sign parameter and weight at each scheduled visit by treatment group, overall SEL-212 and total.

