**10.6. ECG**

For each 12-lead ECG variable the actual value and the change from baseline will be summarized for the scheduled visits by treatment group, overall SEL-212 and total.

A shift table of the number and percentage of patients with normal and abnormal, and clinically significant abnormal values at each scheduled post-baseline visit compared to the normal / abnormal /clinically significant abnormal categorization at baseline will be provided by treatment group for the overall interpretation. A frequency table with number and percentage of patients with abnormal clinically significant overall interpretation will be presented for each scheduled visit by treatment group, overall SEL-212 and total. Additionally, a frequency table with number and percentage of patients with noteworthy QTcF/QTcB values ( $> 450$ ,  $> 480$  and  $> 500$  ms) during the study and of patients noteworthy QTcF/QTcB changes from baseline ( $\geq 30$  but  $< 60$ ;  $\geq 60$  ms) will be provided by treatment group, overall SEL-212 and total.

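### Late-visit laboratory and ECG summaries mix on-drug and long-off-drug values in the SEL-212 arms, with no on-treatment tables beside them

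*SAP*

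**What the plan says.** **Summaries.** For laboratory data, SAP 10.4 says: "Each laboratory parameter will be summarized by scheduled visit and by treatment group, overall SEL-212 and total, presenting actual values and change from baseline". It adds shift tables at each scheduled post-baseline visit. Protocol 13.5.3 matches: "Laboratory data will be summarized by the type of laboratory test and will be presented for each scheduled visit stratified by treatment group and overall". For ECG, SAP 10.6 says: "For each 12-lead ECG variable the actual value and the change from baseline will be summarized for the scheduled visits by treatment group", again with shift tables; Protocol 13.5.5 matches. SAP section 10 bases safety analyses on the Safety Set, which SAP 5.2 groups by treatment received, so a SEL-212 patient who stops stays in the SEL-212 column. None of these sections restricts values by time since the last dose.

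**Visits after stopping.** Protocol 7.1.3: "If withdrawn from study drug, regardless of reason, the patient will continue study visits to the end of Treatment Period 6". Safety laboratory samples are due on Day 21 of TP2-TP5 and on Day 21 and Day 28 of TP6 (Protocol 7.1.2).

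**Contrast with adverse events.** SAP 10.3 gives treatment-emergent events an end point: "until the End of Study Visit (30 days after completion of the last dose of study drug". A last-on-treatment measurement is mentioned only in the unscheduled-visit rules of SAP 7.4. No table in SAP section 10 uses it.

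**Who is stopped.** The sUA rule (Protocol 7.4.1.1, SAP 3.3) needs sUA below 2.0 mg/dL one hour after the TP1 infusion, together with a Day 21 value above 1.0 mg/dL in TP1 or above 6.0 mg/dL in TP2-TP5. Patients enter with screening sUA of at least 7 mg/dL.

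**The concern.** Saline would not bring sUA from at least 7 mg/dL to below 2.0 mg/dL within hours, so the rule in practice stops only SEL-212 patients. Placebo patients can come off drug by other routes, such as a missing Day 21 sUA, but their values carry no drug effect to dilute. The mixing therefore matters only in the active columns, and it grows with each period.

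At stake is how the safety tables read over time. Protocol 7.6.3.2.2 already argues from Phase 2 that adverse events were most frequent after the first cycle and that risk did not appear to rise with repeated exposure. By-visit laboratory tables could show the same fading partly because patients had stopped, and the planned tables could not separate the two explanations.

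**Working it through.** **The plan's own figure.** The documents give no figure for this dilution. The planning rate used below as a bound comes from Protocol 13.1: "the responder rate in all randomized and dosed patients is assumed to be 45% in SEL-212". The sample size built on it reproduces: 45% vs 5%, two-sided alpha 2.5%, 90% power and a continuity-corrected chi-square test give 32 per arm. Then 32 / (1 - 0.08) = 34.8, rounded up to 35.

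**Step 1: time since last dose.** Doses fall on Day 0 of six 28-day periods. For a last dose in period k, a value on Day d of period m lies 28 x (m - k) + d days after it.

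| Last dose in | TP6 Day 21 | TP6 Day 28 |
|---|---|---|
| TP1 | 161 | 168 |
| TP2 | 133 | 140 |
| TP3 | 105 | 112 |
| TP4 | 77 | 84 |
| TP5 | 49 | 56 |
| TP6 (still on drug) | 21 | 28 |

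The first Day 21 visit after a missed dose has m - k = 1, so it lies 28 + 21 = 49 days after the last dose. TP1 Day 21 is unaffected, because no rule-stop has yet taken effect; mixing can begin at TP2 Day 21. On the nominal calendar, every scheduled Day 21 or Day 28 laboratory value from a stopped patient after a missed dose is 49 days or more from the last dose, and every such value from a dosed patient is 28 days or less.

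**Step 2: ECG.** As the schedules read (Protocol Appendix A, SAP Table A), the one scheduled post-baseline ECG apart from early termination is at the end of TP6. For a rule-stopped patient that is at least 56 days after the last dose.

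**Step 3: dilution.** Let f be the share of SEL-212 patients with a value at the visit who are off drug, and suppose the effect is gone off drug. Then

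arm-mean shift = (1 - f) x on-drug shift.

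The documents do not give f. Proxies from them:

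- Protocol 7.6.3.2.1 reports week-12 sUA control of 61% in Cohort 13 and 67% in Cohort 17, both listed among the Phase 3 dose regimens. Non-control is 39% and 33%.
- The planned 45% response leaves 1 - 0.45 = 55% non-responders. This is an upper bound at that response rate.

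| f | Off drug, of 47 | Share of on-drug shift shown |
|---|---|---|
| 0.33 | 15.5 | 67% |
| 0.39 | 18.3 | 61% |
| 0.55 | 25.9 | 45% |

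**The case against.** The strongest reply is that the important signals are captured elsewhere. Hyperlipidemia, worsening renal function, proteinuria and leukopenia judged clinically significant are adverse events of special interest (SAP 10.3), with rates per unit of treatment exposure, so off-drug time does not dilute them. Other clinically significant findings become adverse events (Protocol 12.2.2.6), and abnormal values are listed (SAP 10.4). Stopping-rule counts and treatment terminations are tabulated by period (SAP 10.1, 8.1). All of this stands and lowers the stakes. None of it gives a mean change or shift table for patients on drug.

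Several stronger readings are tempting but not supported:

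- A reader might infer that all known rapamycin effects were transient in Phase 2. Protocol 7.6.3.2.1 says so only of hyperglycemia, hypophosphatemia and hypertriglyceridemia, and does not tie resolution to stopping drug. Reversal off drug is an assumption.
- A reader might infer a loss of power for a safety comparison. The plan attaches no test or confidence interval to laboratory changes, and the Phase 2 event percentages are whole-study incidences, not rates at a visit.
- A reader might take the 55% as an estimate. It treats every non-responder as off drug yet still giving samples. The planning definition of failure includes consent withdrawal and loss to follow-up, and a patient who loses control only in TP6 has had all six doses.
- A reader might extend the point equally to vital signs. Those timed to infusions exist only for dosed patients, so they are little affected. Nor do the documents report an ECG effect of rapamycin; for ECG the point is timing.
- A reader might conclude that on-treatment tables should replace the planned ones. They would compare SEL-212 patients who stayed on drug with nearly all placebo patients, a selected contrast that can also make toxicity seem to fade.

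**Conclusion.** The point holds for laboratory and ECG summaries as a gap that is cheap to close. Followed exactly, the plan mixes on-drug values with values 49-161 days (TP6 Day 21) or 56-168 days (TP6 Day 28) after the last dose in the SEL-212 columns. For any effect that reverses off drug, the bias at late visits is toward placebo.

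The size is not established. The 61-67% range assumes full reversal and takes week-12 non-control in Cohorts 13 and 17 as a stand-in for stopping; 45% is the floor under the planned response rate. An effect that persists off drug would be diluted less. An effect that fades despite continued dosing would show real fading, which the all-data tables could not tell apart from stopping.

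**What to change.** Keep the all-data by-visit tables. In SAP 10.4 and 10.6, add for laboratory parameters and ECG:

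1. On-treatment by-visit summaries and shift tables, using values from first dose to 30 (+4) days after the patient's last dose. The +4 matches the safety follow-up window. It matters because the TP6 Day 28 visit may fall on Day 31, which a strict 30-day limit would drop for a fully dosed patient.
2. A last-on-treatment row per parameter, so that patients who stopped early still contribute an on-drug value.
3. The number of patients on and off drug at each visit. The n already planned in SAP 7.1 does not make this split.

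State also how the window treats a period extended toward the 90-day maximum, where a patient still on study drug may have values beyond it.

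The cost is SAP wording, one dataset flag and a few more tables. Late-visit numbers in the on-treatment SEL-212 columns will be smaller, and that group is selected, so these tables should be read beside the all-data ones. No dose, visit or stopping rule changes.

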Gout flares will be assessed at each study visit during the Treatment Phase using a validated definition of flares in patients with established gout ([Gaffo 2018](#)). In addition, in an exploratory manner, gout flares will be self-assessed by the patient weekly after randomization and in each Treatment Period using a weekly flare diary ([Poiley 2016](#)). Patient reported outcome measures (PROs), tophus burden and joint swelling and tenderness will be assessed on Day 0 of Treatment Periods 1 and 4, and at the end of Treatment Period 6 or early termination (ET) if a patient discontinues the study prior to the end of 6 monthly infusions. Samples for anti-uricase, anti-PEG, and anti-pegadricase antibody levels will be taken (i) prior to administration of study drug dosing and at Day 21 for each of the six treatment periods throughout the trial and (ii) at the end of Treatment Period 6 or at ET. Exploratory assessments of inflammatory/immunologic biomarkers and multiomic analysis will also be assessed.

[figure not shown]
Safety laboratory samples, consisting of, but not limited to, complete blood count (CBC) including white blood cell count (WBC) and absolute neutrophil count; liver function tests (LFTs) including aspartate aminotransferase (AST) and alanine transaminase (ALT); serum lipids (including triglycerides and low density lipoprotein (LDL)), analyses of renal function including creatinine, urine albumin creatinine ratio (UACR), and estimated glomerular filtration rate (eGFR) will be collected on Day 0 and Day 21 of Treatment Period 1, on Day 21 only of each of Treatment Periods 2-5, and on Day 21 and Day 28 / ET of Treatment Period 6. On Treatment Period 1 Day 0, safety laboratory samples will be collected pre-infusion in both the SEL-212 arm and the placebo arm. Concomitant medications and procedures and adverse events (AEs) will be monitored continuously during the study. Post-Baseline chest X-rays (CXR) will be taken at six months / ET to assess for presence of or changes in interstitial lung disease (ILD) compared to baseline CXR.

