Appendix A Schedule of Assessments, continued

Assessment	Scr. - 45 d to D0 (Pre-dose) ³	Treatment Phase														EOS ¹	ET
		TP1 ²		TP2 ²		TP3 ²		TP4 ²		TP5 ²		TP6 ²					
Day	D0	D21	D0 ⁵	D21	D0 ⁵	D21	D0 ⁵	D21	D0 ⁵	D21	D0 ⁵	D7 ⁴	D14 ⁴	D21 ⁴	D28		
Tophus Assessment/Photography	X							X								X	X
Gout Flare Assessment ²²	X	X	X	X	X	X	X	X	X	X	X	X	X	X	X	X	X
Gout Flare Weekly Diary		Continuously on Weekly Basis ²³															X
Joint Assessment (tenderness, swelling)		X						X								X	X
Health Questionnaires ²⁴		X						X								X	X
Collect Sample for sUA	X	Refer to Schedule of Assessments (Appendix B) for sUA Sample Collection during Treatment Phase															X
PD/Uricase Activity Assessment		Refer to Schedule of Assessments (Appendix B) for PD/Uricase Activity Assessments during Treatment Phase															X
Study Drug Administration		Refer to Schedule of Assessments in Appendix B for Study Drug Administration during the Treatment Phase															
Infusion Reaction Follow-up		Refer to Section 12.2.1.5															
Concomitant Medications / Procedures		Continuously														X	X
AE Collection		Continuously														X	X
SAE Collection		Continuously														X	X

1. Phone call at 30 (+4) days after the last study drug infusion for assessment of concomitant medications/procedures, AEs, and SAEs.
2. Visit window at Day 21 of each Treatment Period is +2/-1 days; visit window at Day 7 and Day 14 of Treatment Period 6 is +2/-1 days; visit window at Day 28 of Treatment Period 6 is +3/-4 days.
3. Visit window is -2 days.
4. Assessments at this visit are permitted to be performed remotely (inclusive of collecting applicable lab draws and assessments per protocol visit windows).

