## 7. General Aspects for Statistical Analysis

### 7.1. General Methods

SAS® version 9.4 or higher will be used for all statistical analyses and tabulations.

In general, summaries will present data by treatment group and overall for each scheduled assessment time where appropriate.

Unless stated otherwise, descriptive summaries will include n, mean, standard deviation, median, minimum and maximum for continuous variables, and n and percent for categorical variables. If there are multiple assessments collected for the same scheduled time the first assessment post-baseline will be used. The last available assessment before start of study treatment will be used as baseline.

Adverse events and medical history will be coded according to the most recent version of Medical Dictionary for Regulatory Activities (MedDRA). Prior and concomitant medications will be coded using the most recent WHO Drug Dictionary version. The actual version of MedDRA and WHO drug used will be noted in the footnote of the respective output.

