#### **7.4. Unscheduled visits**

Unscheduled visit measurements will be included in analyses and treatment summaries in the following circumstances:

- i) If there are missing data at a scheduled visit, but data available at an unscheduled visit that occurred after the previous scheduled visit, and prior to the next scheduled visit.
  - a. In the event there are more than one unscheduled visit between the previous scheduled visit and the next scheduled visit, the closest measurement to the missed target day will be used.
  - b. If there are multiple records within the same distance from the target day, the latest record will be used.
- ii) Derivations of baseline/last-on-treatment measurements.
- iii) For all safety parameters, if there are multiple measurements within a visit window, then the record closest to the target day will be used.
  - a. In the event there are more than one unscheduled visit between the previous scheduled visit and the next scheduled visit, the closest measurement to the missed target day will be used.
  - b. If there are multiple records within the same distance from the target day, the latest record will be used.

Otherwise, data collected at unscheduled visits will be included in the data listings but will not be included in the analyses or in treatment summaries.

This document is confidential.

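### SAP 10.4 tabulates safety labs only visit by visit, so the planned lab tables cannot in general show how many patients per arm ever became abnormal or reached a given level

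*SAP*

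**What the plan says.** SAP 10.4 summarizes each laboratory parameter by scheduled visit, as actual value and change from baseline. It adds "Shift tables of the number and percentage of patients below normal range (low), within normal range (normal) and above normal range (high"), one for every planned visit after baseline and set against the baseline category, and a listing of clinically significant abnormal results. Protocol 13.5.3 has the same content: by-visit summaries, and shift tables of "low/normal/high (or normal/abnormal, as appropriate) values at each scheduled post-baseline visit". Under SAP 7.1 the "descriptive summaries will include n, mean, standard deviation, median, minimum and maximum for continuous variables", so by-visit extremes will be shown.

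Two sets of rules decide which record enters a table:

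- SAP 7.1: "If there are multiple assessments collected for the same scheduled time the first assessment post-baseline will be used".
- SAP 7.4, for safety parameters: "if there are multiple measurements within a visit window, then the record closest to the target day will be used". Unscheduled values also enter when a scheduled value is missing, or to derive baseline or last-on-treatment values. Otherwise "data collected at unscheduled visits will be included in the data listings but will not be included in the analyses or in treatment summaries".

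On timing, Protocol 7.1.2 takes safety labs on Day 0 and Day 21 of Treatment Period 1, then "on Day 21 only of each of Treatment Periods 2-5, and on Day 21 and Day 28 / ET of Treatment Period 6".

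Laboratory abnormalities also reach the adverse event tables. Protocol 12.2.2.6 makes clinically significant findings, or significant worsening from baseline, reportable. SAP 10.3 treats hyperlipidemia, worsening renal tests, proteinuria and leukopenia as events of special interest if the investigator judges them clinically significant.

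**The concern.** Comparing the safety of SEL-212 with placebo is a stated objective, and the two active arms differ only in the SEL-110.36 (rapamycin) dose. A natural question is how many patients in each arm ever had, say, a low white cell count or a marked rise in triglycerides. A set of by-visit tables does not answer it, because the same patient may appear at several visits and the visit counts cannot be added.

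Two features widen the gap. A high or low result at an extra visit normally goes only to listings. And the shift categories show direction but not degree: the entry criteria admit fasting triglycerides up to 500 mg/dL, LDL up to 200 mg/dL and fasting glucose up to 240 mg/dL, so a patient already above normal at baseline stays in the high-to-high cell however far the value climbs.

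The analytes matter for this product. Protocol 7.6.3.2.1 reports hypertriglyceridemia in 17.8%, leukopenia in 7.2%, hyperglycemia in 5.9%, and neutropenia and hypophosphatemia in 3.9% each of Phase 2 patients. It describes the three metabolic events as transient and without serious consequences, which limits their clinical weight.

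**Working it through.** The plan states no figure on this point, so there is none to reproduce. The check has three parts.

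**1. Which planned outputs count a patient once?**

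| Output | Unit | Gives an ever-abnormal lab count? |
|---|---|---|
| SAP 10.4 summaries | visit | No; the minimum and maximum show only whether anyone passed a level at that visit |
| SAP 10.4 shift tables | patient within visit | No |
| SAP 10.4 and SAP 10 listings | record | Only by hand count |
| SAP 10.3 adverse event tables | patient | Only for events the investigator reports; no numeric level |
| SAP 10.1 stopping-rule counts | patient | No; these concern serum uric acid control |
| SAP 10.6 QTc limits | patient, during the study | Not a lab output |

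**2. Which record is used?** The SAP 7.1 rule takes the first record and the SAP 7.4 rule the one nearest the target day. Neither takes the worst. An unscheduled value outside the exceptions in SAP 7.4 does not reach a laboratory summary or shift table.

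**3. How loosely do by-visit counts fix the number of different patients?**

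Inputs:

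- Visits V: Day 21 of Treatment Periods 1 to 6 (6) plus Day 28 of Treatment Period 6 (1) = 7 (Protocol 7.1.2).
- Patients per arm N: about 47 (SAP 3.4), taken here as complete at every visit.
- Newly abnormal patients at each visit k: assumed, because the documents give no laboratory distributions.

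The number of different patients D satisfies k ≤ D ≤ min(N, V × k). The lower end means the same patients every time; the upper end means no overlap. If visits were independent, the expected value would be N × [1 − (1 − k/N)^V].

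- k = 1: lower 1/47 = 2.1%; upper 7/47 = 14.9%; independent 47 × [1 − (46/47)^7] = 6.57, or 14.0%.
- k = 3: lower 3/47 = 6.4%; upper 21/47 = 44.7%; independent 47 × [1 − (44/47)^7] = 17.38, or 37.0%.

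Laboratory values tend to persist within a patient, and the last two visits are about a week apart, so the truth probably lies below the independence figure. The by-visit tables do not show where.

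**The case against.** The strongest reply is that this is a reporting preference. SAP 10.4 matches the protocol, nothing in either document requires a worst-value table, and SAP 10.3 already gives much of what is wanted: patient counts, maximum intensity, exposure-adjusted rates by patient and by event, and rate differences with 95% confidence intervals for events of special interest seen in at least 2% of patients. Investigator reporting also produced usable per-patient figures in Phase 2. By-visit minima and maxima answer the question in one case: if the maximum stays below a level at every visit, no patient reached it at a visit included in the summaries.

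Most of this stands and limits the point, but it does not remove it. The adverse event route depends on clinical judgement and carries no numeric level. Hyperglycemia and hypophosphatemia are not on the special-interest list.

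A reader might infer that laboratory adverse events will be under-reported. The documents do not show that. A reader might also infer that most changes between visits are being discarded. That does not follow either: scheduled safety labs fall almost entirely on Day 21, most other days have no sample, and a new table can add only unscheduled values that exist, whose number is unknown.

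The comparison with QTc, which does get a count against fixed limits, is weak support. As far as the schedule can be read, there is about one post-baseline ECG, so that count pools little.

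**Conclusion.** The gap is real and modest. The planned laboratory tables cannot in general state how many patients per arm ever became abnormal or reached a given level, and they hide further rises in patients already high at baseline. This rests on reading SAP 10.4 together with SAP 7.1 and 7.4, and does not depend on the illustration.

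The ranges of 3 to 21 patients (6.4% to 44.7%) and 1 to 7 (2.1% to 14.9%) assume k, 47 patients per arm and complete attendance. They show how little the by-visit counts determine; they are not estimates of anything missed. The count could be recovered from listings or datasets, but no table is planned. Efficacy conclusions are untouched. This is an inexpensive improvement to descriptive safety reporting, not a fault in validity.

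**What to change.** In SAP 10.4 add one compact table, by arm and for overall SEL-212, of baseline versus worst post-baseline category, counting each patient once. Cover WBC, neutrophils, triglycerides, LDL, fasting glucose, phosphate, creatinine/eGFR, UACR and ALT/AST.

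- **Categories:** the normal range plus the protocol entry limits. Use Rheumatology Common Toxicity Criteria v2.0 numeric grades where they exist; the protocol already uses that scale for adverse events, but the documents do not reproduce the grades.
- **Degree:** the largest change from baseline per patient, so that a rise within the high category is visible.
- **Records:** include unscheduled values, as a stated exception to SAP 7.4. Repeat the table for scheduled visits only as a check.

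Keep the by-visit and adverse event tables as they are.

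The cost is SAP wording and a few extra outputs from data already collected, with no new sampling. The main downside is uneven ascertainment: infusion reactions trigger extra chemistry and hematology samples (Protocol 10.7) after steroid premedication (Protocol 10.6.2), which can itself affect glucose and WBC. A footnote should say so, and the scheduled-only version lets the reader judge its influence.
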